Please note that Epidiolex is FDA approved for the treatment of seizures in Lennox-Gestaut syndrome and Dravet syndrome and is clinically used for the treatment of seizures in Sturge-Weber syndrome and many other medically refractory seizure disorders[1-3]. Epidiolex is **no longer** scheduled and can be prescribed clinically for patients seen remotely. We are studying Epidiolex here in Sturge-Weber syndrome for different indications.

Hypothesis: Cannabidiol (Epidiolex) improves SWS brain function resulting in improved cognitive function, social interactions, mood, motor function and behavior, as well as reduced migraines.

2. Objectives (include all primary and secondary objectives)

We propose a follow up to the initial SWS Epidiolex study which suggested improvements in SWS cognitive, social, and behavioral function and in other neurologic issues. **Primary outcome measure:** Quantify cognition 6 months after initiation of Epidiolex compared to baseline. **Secondary outcome**

measures: The following at 6 months compared to baseline: Social function and mood, frequency and severity of seizures, migraine frequency and severity, and motor outcomes.

3. Background (briefly describe pre-clinical and clinical data, current experience with procedures, drug or device, and any other relevant information to justify the research)

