When recruiting participants, the frequent visit schedule will be reviewed with the participants to ensure they are aware of the time commitment required to be in this study. All visits will be scheduled as far in advance as possible and will occur remotely by utilizing a video conference application Participants will receive reminders via email or phone before their appointments. All appointments surrounding holidays and travel will be scheduled far in advance.

Anticipated numbers of subjects to be enrolled and on study drug:

	American	Asian	Black,		White,		
	Indian or	or	not of	Hispanic	not of	Other or	Total
	Alaskan	Pacific	Hispanic		Hispanic	Unknown	
	Native	Islander	Origin		Origin		
	0	1	1	0	3		5
Female							
	1	0	0	1	3		5
Male							
	1	1	1	1	6		10

Total				

Written Informed Consent

Written informed consent will be obtained from each participant before any study-specific procedures or assessments are done and after the aims, methods, anticipated benefits, and potential hazards are explained. The participant's willingness to participate in the study will be documented in writing in a consent form, which will be signed by the participant or legal guardian with the date of that signature indicated. The investigator will keep the original consent forms and signed copies will be given to the participants. It will also be explained to the participants that they are free to refuse entry into the study and free to withdraw from the study at any time without prejudice to future treatment.

Process of Consent

The investigational nature and objectives of this trial, the procedures, the treatments involved, the attendant risks, discomforts, and potential benefits, as well as potential alternative therapies, will be carefully explained to the patient or their parents or guardian if he/she is a child. A signed informed consent document will be obtained after the entirety of the pilot study is explained. Consent will be obtained by the co-investigator designated to obtain consent on the IRB and delegation log for the trial. Where deemed appropriate by the clinician and the child's parents or guardian, the child will also be included in all discussions about the trial and assent obtained where appropriate.

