Baseline behavioral profiles will also be obtained by using age-appropriate, well-established standardized instruments commonly used in neuropsychiatry clinical practice. These instruments may include the Behavioral Assessment System for Children (BASC), The Screen for Child Anxiety Related Disorders (SCARED) or Children's Depression Rating Scale (CDRS). A quality of life scale is also expected to be obtained such as the Quality of Life in Epilepsy Scale for adolescents (QOLIE-ad-48).

The use of these instruments will reveal a sophisticated behavioral and psychiatric profile that is the state of the art in clinical behavioral science research. Baseline behavior function and psychiatric diagnoses will be well established prior to treatment and compared to ratings from behavioral profile scales obtained at a follow up stage (Approximate time-3 hours at baseline, 1 hour at follow-up).

Safety of Epidiolex: as measured by the number of adverse events and serious adverse events resulting from study drug.

Change in Seizure Severity: All seizure types will be classified before study entry (most common seizure type are partial motor and partial with impaired consciousness). Seizure frequency for each seizure type will be recorded retrospectively for the month prior to enrollment and at each visit during the study using diaries. In addition, at each visit the parents/caregivers will report the following secondary outcome measures: seizure duration by seizure type, number of episodes of status epilepticus (defined as convulsive seizure lasting longer than 10 minutes), number of uses of rescue medication, and the number of ER visits/hospitalizations.

Change in motor function, as defined by Modified House Classification and selected scales from EDPA and parent-report measures: PEDI-CAT and ABILHAND/ABILHAND-KIDS (as previously described).[30] Video recordings of the Modified House Classification and selected scales from EDPA will be taken for each subject at baseline and at six months follow-up. The video recordings will be reviewed and scored blind by a study team occupational therapist. Administration time: 20 minutes

Laboratory tests and clinical procedures

- 1) Weight and vitals will be monitored at baseline and at each remote visit. (Routine care).

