- 6) hCG urine pregnancy test will be used for all female participants Tanner stage 2 and above (see Study Visit Table). We will tell subjects that they must be using effective birth control (for example, abstinence, birth control pills, contraceptive implants, condoms) and confirm that this is the case at each study visit. We will inform female subjects that they should not become pregnant or breastfeed a baby while on this study or for 12 weeks after taking Cannabidiol. We will also inform male subjects that they should not get their partners pregnant while on this study or for 12 weeks after taking Cannabidiol. Anyone who becomes pregnant while on the study will be removed immediately.

Case Report Forms: Forms generated for use as case report forms will also be used as source documents. Forms will be filled out during the study visit with data. Immediately after the visit, the form will be photocopied and one copy will immediately have the study subject ID# written on it (case report form). The other copy will immediately have the subject name written on it (source document).

b. Study duration and number of study visits required of research participants.

Duration of therapy: Study duration for subjects will be between 6 months to 2 years depending on the age at enrollment. During the study, subjects will be seen at 1 month, 3 months and the every 3 months until they are 2 years of age. Therefore the number of study visits will range from 4 to 8, again depending on the age at enrollment. Total length of study for completion of all subjects will be 4 years as outlined in the Milestones Table attached. Once the optimal dose is found (20 mg/kg/day or maximal tolerated dose; expected to be reached within 4 weeks), participants will continue on the Core Phase until 2 years of age. At the end of the core phase, cognitive and all other testing will be repeated. **Total duration for each subject= until 2 years of age, a minimum of 6 months and 5 visits.**

Study Visit 1: Screening Visit- Informed consent process, eligibility criteria reviewed. The following tests are done at *visit one*, *or at or before visit 2* (maximum of two weeks between visits 1 and 2): baseline developmental testing, baseline labs sent, neurological exam, and baseline motor testing, Quality of life measures, motor testing video, Neuroscore and Port-wine birthmark score.

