Sharing of test results: This study involves tests, labwork, that could be useful for the clinical care of the subject. We will share this information with the subject if clinically significant abnormalities are seen. If for example, if the labwork is significantly abnormal, then [name] will contact the subject tell them what to do. If the evaluation of mood suggests that urgent treatment is required, then [name] or [name] will speak with them about what the next step should be. The other research tests are not expected to produce results that would be relevant for clinical care, so we will not share these results with the subject.

Data Management

The trial PI will review the study progress weekly. Patients entered on the trial and adverse events will be reviewed to ensure that the study is implemented as outlined in the protocol. Data will be collected on case report forms. Monthly reports will be generated to assess completeness of data. There will be monthly phone conferences to address quality assurance (QA) issues.

The trial database will use a system of coded identifiers to protect participant confidentiality and safety. Each participant enrolled will be assigned a research identifier by the KKI.

Study Records Retention

Patient files will be kept until at least seven years after completion of the study.

c. Blinding, including justification for blinding or not blinding the trial, if applicable.

During this phase II trial, where the primary objectives are to assess novel treatment targets and tolerability, blinding is not appropriate.

d. Justification of why participants will not receive routine care or will have current therapy stopped.

Participants will otherwise receive routine care and will not have to stop any of their current anticonvulsants or other medications. They will be clinically managed by [name] who will respond to side effects or worsening of the participants' care in a manner consistent with the participants' best interest, including the removal of the participant from the trial.

e. Justification for inclusion of a placebo or non-treatment group.

Not applicable for this trial.

f. Definition of treatment failure or participant removal criteria.

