An earlier study of Epidiolex for medically refractory seizures in Sturge-Weber syndrome suggested improvement in cognition, social, and behavioral outcomes. The side effects experienced were mild and transient.

The proposed trial will be assessing the impact of Epidiolex upon cognitive impairment in Sturge-Weber patients.

c. Justification and safety information if non-FDA approved drugs without an IND will be administered.

Not applicable.

7. Study Statistics

a. Primary outcome variable.

Change in cognitive impairment: Combined score of two NIH Toolbox subtests.

b. Secondary outcome variables.

Change in the following:
SWS neuroscore
Port-wine score
Adverse Events
Seizure severity
Social, behavioral, and mood function
Migraine severity
Motor function

c. Statistical plan including sample size justification and interim data analysis.

Statistical Plan: Results of the above tests will be compared to age normed values. In addition, the difference in results between final test results and initial test results will be obtained for the cognitive functioning score of each subject. Mean and standard deviation of this difference for all 10 subjects on study drug will be calculated. These results will be used to determine whether individuals and the group as a whole demonstrated age normed changes in their cognitive functioning over the course of the six month trial. There is no control group in this study of subjects who are not receiving study drug. The published test-retest standard deviations will be used to determine whether changes in testing results exceed expected test-retest changes in results.

Sample Size Calculation: Since these outcomes will be done for the first time with this drug in SWS, a sample size calculation was not done. Rather, we are estimating that 10 subjects enrolled and on study drug will be sufficient to do the proposed pilot trial and show improvements (or trends for improvement) sufficient to design a future larger clinical trial, or to guide clinical care. This estimate is based on our experience with another trial using the same primary outcome measure.

Interim data analysis: Every week [name] and the study coordinator study will review data for safety. Each month, a formal review of recruitment, safety, data completion and study progress will be made. An

assessment of progress as it relates to study milestones (see **Milestone Table** below) will be made, and a summary report prepared for Greenwich Biosciences.

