Other Assessments: Procedures involved in this study include cognitive testing, motor, mood, behavior, and social function evaluations, assessment of migraine severity. All of the above procedures may be considered boring or tiring to the participant, especially children.

Time Commitment: There is a time commitment for participants attending the required appointments and maintaining seizure diary/records. The first two appointments will take about 3 hours, follow up visits 1-2 hours and the final visit 3-4 hours. Participants will also be asked to maintain a seizure diary and study drug dosing record, requiring a time commitment of about 5-10 minutes per day.

Confidentiality: There is also the risk of loss of confidentiality in allowing us to see medical information and use it for research purposes.

b. Steps taken to minimize the risks.

PI Oversight: The Principal Investigator, [name], will review all data relating to safety and tolerability throughout the study. The study will benefit from her two decades of experience treating participants with Sturge-Weber syndrome as the director of the Hunter Nelson Sturge-Weber Center. The investigator will be available by telephone, text, or email throughout the entire study.

Training: Training will be provided by [name] and the other clinician investigators to all nursing and research staff who will be involved in the drug trial. This training will be documented and updated as needed.

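### Baseline seizure frequency is a retrospective record and on-study frequency comes from diaries, so the uncontrolled change in per-type seizure frequency can contain a method difference of unknown size and direction

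*Combined protocol and SAP*

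**What the plan says.** Section 2 lists the secondary outcomes as "The following at 6 months compared to baseline: Social function and mood, frequency and severity of seizures, migraine frequency and severity, and motor outcomes". Section 7b repeats "Seizure severity" among the changes to be assessed. Section 7c gives no estimator, time window or test for it.

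The measurement rule is in Section 4a, Change in Seizure Severity: "Seizure frequency for each seizure type will be recorded retrospectively for the month prior to enrollment and at each visit during the study using diaries". Section 8a (Time Commitment) adds: "Participants will also be asked to maintain a seizure diary and study drug dosing record". Neither section says on what date the seizure diary is handed out.

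Three other provisions bear on the point:

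- **Consent** (Section 4a, Written Informed Consent): "Written informed consent will be obtained from each participant before any study-specific procedures or assessments are done".
- **Pre-drug interval** (Section 4b, Study Visit 1): "maximum of two weeks between visits 1 and 2". Section 4a adds that the drug is shipped to the home within 1 week of prescription at the baseline visit.
- **Design**: Section 7c says "There is no control group in this study of subjects who are not receiving study drug", and Section 4c says "blinding is not appropriate".

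**The concern.** A before-after change can be read as a change in seizures only if both ends are measured the same way. Here the pre-drug end is a retrospective account of one month, and the on-study end is a count from a diary kept as events happen. The two methods may not capture the same share of seizures. In a trial with a comparator, both arms would switch method together and the difference would largely cancel. Here each subject is the only control, so the difference adds to, or subtracts from, any drug effect, and no later analysis can separate the two.

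At stake is the seizure-frequency part of a named secondary outcome. Section 11 (Limitations) gives size and the lack of a placebo group as the main limitations and does not mention the change of method.

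**Working it through.** The plan has no figure to reproduce: Section 7c says no sample size calculation was done, and no seizure rate or seizure effect size is given. The check is therefore a reading of the text followed by an illustration on assumed values.

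**Step 1. Which method covers which period?**

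| Period | Source named in the protocol |
|---|---|
| Month before enrolment | Retrospective record (4a) |
| Visit 1 to Visit 2, before drug | Seizure history at both visits (visit table); diary start date not stated |
| On drug, visits at weeks 4, 12 and 24 | Diaries (4a, 8a) |

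Section 4a allows no study procedure before consent, so a study diary cannot cover the month before enrolment. A diary for that month would have to be one the family already kept, which the protocol does not ask for.

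**Step 2. How does a capture difference enter the change?** Let c be the rate found by the retrospective record divided by the rate a diary would have found for the same month. Let RR be the true rate ratio, on drug versus before.

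Apparent change = RR / c - 1

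The values of c are assumptions; the documents give none.

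| c | No drug effect (RR = 1) | True halving (RR = 0.5) |
|---|---|---|
| 0.7 | 1/0.7 - 1 = +43% | 0.5/0.7 - 1 = -29% |
| 0.8 | 1/0.8 - 1 = +25% | 0.5/0.8 - 1 = -37.5% |
| 1.0 | 0% | -50% |
| 1.2 | 1/1.2 - 1 = -17% | 0.5/1.2 - 1 = -58% |
| 1.3 | 1/1.3 - 1 = -23% | 0.5/1.3 - 1 = -62% |

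The artefact can hide a benefit or create one.

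**Step 3. What could it do in a group of 10?** Assume Poisson counts, equal one-month windows, no drug effect and a diary-equivalent rate of 10 per month. A drop of at least 50% is used only as a yardstick; the protocol sets no responder definition.

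| c | One subject shows the drop | 3 or more of 10 do |
|---|---|---|
| 1.0 | 8% | 5% |
| 1.25 | 17% | 22% |
| 1.5 | 28% | 55% |

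At 30 per month and c = 1.25, the same figures are 4% and 0.5%. The effect on such counts therefore depends heavily on seizure rate as well as on c.

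**Step 4. What pre-drug diary time does the schedule allow?** Visits 1 and 2 are at most 14 days apart. Up to 7 days of shipping gives at most 14 + 7 = 21 days. Both are ceilings and no minimum is set, so a full 28-day diary baseline does not fit the present schedule. At an assumed 4 seizures per 28 days, the Poisson chance of a zero baseline is exp(-2) = 13.5% over 14 days and exp(-3) = 5.0% over 21 days. Percent change is undefined in those subjects.

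**Step 5. Are the windows equal?** Baseline is one month. The last on-drug interval, week 12 to week 24, is 12 weeks, or 84/28 = 3 periods of 28 days. No window is defined for the 6-month seizure value, so counts need a common rate.

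**The case against.** **The sentence is ambiguous.** The reference to diaries can grammatically govern both periods. Subjects come largely from the centre's own patients and research databases, so family diaries or clinic records may exist. This stands in part: a reader might infer that baseline is a one-month recall, but the protocol says only that it is recorded retrospectively and does not name the source. It still requires no diary for that month. If one was intended, the text should say so.

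**The pre-drug interval may already be covered.** A reader might infer that the days between Visits 1 and 2 go unused. The documents do not support that. Visit 2 is a study visit before drug, Section 4a calls for diary recording at each study visit, and the visit table lists seizure history at both visits. What is missing is the diary's start date and the window that counts as baseline.

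**Other seizure measures use one method throughout.** The neuroscore, which includes seizure frequency, is assigned at every visit. Seizure duration, status epilepticus, rescue use and emergency visits or hospital stays are caregiver-reported at each visit. This stands and confines the problem to the per-type frequency count. The source of the neuroscore's seizure component is not stated.

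**Cognition.** The Abstract raises better seizure control as a possible reason for the cognitive gains in the earlier five-patient trial, so a reader might infer that this artefact also distorts the cognitive result. It does not: the primary outcome is measured separately, and Section 7c plans no seizure-adjusted analysis of cognition.

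**The size is algebra on an assumed ratio.** True. The figures show sensitivity; they do not show that bias is present.

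**Conclusion.** The point holds for one quantity: the change from baseline in per-type seizure frequency. On the natural reading, its two ends are measured by different methods, and without a control arm the difference in capture cannot be told apart from a drug effect. Direction and size cannot be found from the documents. On assumed ratios of 0.8 and 1.2, with no drug effect, the apparent change would be +25% and -17%.

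The conclusion rests on two things: that the diary phrase applies to the study period only, and that the baseline month has no diary behind it for at least some subjects. If every family already kept an equivalent diary, c would be close to 1 and the artefact would be small. The primary outcome and the seizure items collected uniformly at each visit are outside the point. It is a cheap improvement to a secondary outcome, not a flaw in the trial's main result.

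**What to change.** 1. State the source of the baseline seizure count, the date the diary is issued, and the windows used for baseline and for 6 months.
2. Issue the existing seizure diary at Visit 1 and record the pre-drug diary days: up to 14 between Visits 1 and 2, plus any days until drug arrives.
3. Ask the same one-month retrospective question at the 6-month visit.
4. Report two like-for-like changes: retrospective to retrospective over equal one-month windows, and diary to diary as a rate per 28 days. Do not rely on the retrospective-to-diary change alone.

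The cost is handing over an existing form earlier and asking one more question. Each comparison has a weakness. The diary baseline is short and may be zero when seizures are infrequent. The 6-month retrospective answer may be influenced by months of diary keeping. Choosing between them trades possible bias against noise, so neither should be declared the sole main result.

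Timing limits what can be done. The protocol is dated 29 June 2021, and the Milestone Table planned the last consents for February 2021 and completion for August 2021. For subjects already past Visit 2, only the 6-month question can be added. Where that is also too late, the mismatch should be stated as a limitation beside size and the lack of a placebo group.

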Virtual Written Consent Process: A copy of the IRB approved Informed Consent document will be provided to the participant prior to the teleconsent meeting either via email, fax or previously provided during an in person visit. The person conducting the consent process will conduct the process via telephone or video. The following is a step-by-step teleconsent / remote consent process: After the consent designee and participant or LAR review the consent form, the participant or LAR will be offered the opportunity to ask any questions and have those questions answered. The consent designee will verify the participant or LAR physically signed the consent document either by viewing via video conference, obtaining a photo of the complete signed consent document; or obtaining verbal confirmation from the participant that he/she signed the consent form or agreed to participate electronically. The participant or LAR will sign and date/time the informed consent document. The signed document will then be mailed, emailed or faxed to the consent designee. If the signed consent is emailed or faxed or returned via photo, the participant or LAR will be asked to return the original signed document on their first in person visit. If the informed consent form is mailed to the consent designee by the participant or LAR, the IRB-approved consent designee will sign the copy which they possess after the participant has acknowledged signature on their copy. Once the original is received by the consent designee the copies will be attached to make a single document. Once received, the IRB-approved consent designee signs, dates/times the informed consent document. A copy of the fully signed written consent will be sent to the participant by mail, email or fax.

Estimated Time Commitments for Visits

Baseline Evaluations- Done on Visit 1 or 2 prior to starting drug. Can also be done between Visit 1 and 2 if more convenient for subject. Cognitive testing/assessments: 1 1/2 hours. Psychiatric/Mood: 3 hours. Neurologic Exam, history, picture, neuroscore, birthmark score: 1 hour. Labs: 30 minutes. Total=6 hours.

Visits 3 and 4. Neurologic Exam, history, and neuroscore: 1 hour. Labs: 30 minutes. Total: 1 ½ hours each remote visit

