- 2) **Neuroscores** (as previously described)[31-33] will be assigned at each visit by [name] as per her clinical routine. The SWS neuroscore is comprised the frequency of seizures, extent of hemiparesis, assessment of visual field cut, and degree of cognitive functioning with a total score of 15 possible points. Neurologic exam and general physical exam will also be performed remotely at each visit. (Routine care)
- 3) Participants will be asked at each remote visit about any change in neurologic symptoms. (Routine care)
- 4) For subjects with a facial port-wine birthmark, frontal and profile photograph will be taken under standardized conditions with scoring of the port-wine birthmark (**Port-wine birthmark score**) for percent of face covered, thickness of birthmark, and darkness of birthmark color. Families will be mailed a color chart (see appendix) to hold up next to the subject while photos are being taken. Subjects without any facial port-wine birthmark will only need photographs taken at a single visit to confirm the lack of birthmark. (Research, See Study Visit Table).

Table of Remote Visits	Screening	Baseline	Core	e Phase	Endpoint 6 months		
Visit Number	1	2	3	4	5		
Study Week	-2 ± 14	days 0	4	12 ± 7 days	24 >		
Consent	х						
Physical Exam	Х	Х	Х	Х	Х		
Neuroscore	Х	х	Х	Х	X		
Neuro QoL	Х	Х	Х	Х	Х		
Incl/Excl Criteria	Х	Х	Х	Х	Х		
Past Medical	х						
History Diagnosis of SWS	Х						
Seizure Hx	X	Х	X	X	X		
Previous AED Hx	X				^		
Current Med Hx	Х	х	Х	Х	Х		
Picture Taken		Х			Х		
Rescue Meds	Х	Х	Х	X	Х		
AEDs	Х	Х	Х	Х	Х		
Motor, NP, psychiatric Assessments	<				X ± 7 days		
Labwork							
AED Levels CMP (renal, hepatic)	X		X	X	X X		
CBC	Х		Х	X	Х		
CBD/THC Ratio			Х	X	X		
Urinalysis	Х		Х	X	X		
Pregnancy Test (if applicable)	Х		Х	Х	Х		
Safety							
Adverse Events check		X	X	X	Х		
Safety Calls:		←		Bi-monthly			
Continue or Remove?	х	х	Х	Х	Х		
Patient Reported Outcomes			Х	х	Х		

- 5) CBC, LFT, BUN, creatinine levels, electrolytes, and urinalysis will be measured at each visit (screening, 1, 3, and 6 months on drug). Concomitant AED plasma concentrations will be measured at the same visits. CBD/THC ratio in urine will be measured three times; at the one month visit, at the three month visit, and at the 6 month visit. All lab tests will be done remotely at a site local to the participant and charged to the study budget.

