Study Visit 2: Baseline Visit- Confirm eligibility and begin drug at dose 1 (see Visit Table and Dose Schedule). Provide study drug dosing record and instruct on use. History, exam, Quality of life measurs, have picture taken, and Port-wine birthmark score.

During visits 3 and beyond (see Visit Table)- the participants will undergo clinical neurologic assessments, blood draws for laboratory tests, study drug accountability, concomitant medication survey, adverse event reporting, and study drug administration (see Visit Table for details). Also, Quality of life measures and neuroscore.

Final Study Visit- Repeat all assessments- developmental testing, labs, neurological exam, motor testing, Quality of life measures, motor testing video, Neuroscore, have picture taken, and Port-wine birthmark score. Determine whether subject will continue on Epidiolex or will be weaned off.

Clinical Follow Up: Subject will be seen one month later for clinical follow up whether on or off Epidiolex.

An additional blood draw will also be necessary within 72 hours of a previous blood draw if the most recent result indicates a clinically significant (>3xULN) elevation of ALT or AST. At minimum, the following tests will be repeated: ALT/AST, total bilirubin, and alkaline phosphatase. A GGT test will also be performed at that time. This bloodwork (ALT/AST, total bilirubin, and alkaline phosphatase and GGT test) will also be necessary if: 1) the dose of the study drug dose is increased after the escalation phase, 2) another drug which affects liver function is added, stopped, or has a dose change, or 3) the subject has one or more of the following symptoms without another explanation: fatigue, encephalopathy, nausea, vomiting, right upper quadrant pain or tenderness, abdominal pain or distension, fever, excessive bruising, excessive nose or gum bleeds, or petechia. All trial subjects with elevated LFTs will be followed closely until all abnormalities return to the baseline state as assessed by the investigator with AST/ALT < 3x ULN and will be followed until ALT/AST have normalized and symptoms resolve.

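### The port-wine birthmark score, a secondary outcome, has no blinded reading specified, although paired photographs are scheduled and the motor videos are already scored blind

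*Combined protocol and SAP*

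**What the plan says.** The port-wine score appears as an outcome in section 7b (Secondary outcome variables), under the entry "Port-wine score". Section 4a, Laboratory tests and clinical procedures, item 4, describes how it is obtained: "frontal and profile photograph will be taken under standardized conditions with scoring of the port-wine birthmark" "for percent of face covered, thickness of birthmark, and darkness of birthmark color". Families are mailed a color chart to appear in the pictures. The visit table places the pictures at baseline and at 6 months. Subjects with no facial birthmark are photographed once only, to document that.

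The score is also itemised as part of the visits:
- Section 4a, Estimated Time Commitments for Visits, uses the same line for the baseline and the final evaluation: "Neurologic Exam, history, picture, neuroscore, birthmark score: 1 hour".
- Section 4b, Study Visit 1, ends its list of tests to be done by visit 2 with "motor testing video, Neuroscore and Port-wine birthmark score".
- Section 4b, Study Visit 2 and Final Study Visit, each include "have picture taken, and Port-wine birthmark score".

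On case report forms in general, section 4a states: "Forms will be filled out during the study visit with data".

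For motor function, section 4a (Change in motor function) has video taken at baseline and six months and adds: "The video recordings will be reviewed and scored blind by a study team occupational therapist". Section 4c declines to blind the trial. No section describes a masked, independent or randomly ordered reading of the birthmark.

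**The concern.** Extent, thickness and darkness of a birthmark are judgements, and the plan describes no automated measurement. All subjects receive the drug and there is no control group, so a scorer who knows whether a picture is from before treatment or from 6 months on drug could, without intending to, create or hide change. Nothing else in the design would separate that from a true effect.

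An expectation of benefit is plausible. Section 6a counts an action on abnormal blood-vessel growth among the drug effects expected to help in this syndrome, and section 3 notes that port-wine birthmarks carry the same mutation.

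The Limitations paragraph in section 11 says the trial is meant to find out which outcome measures serve best for a later randomised trial. A score with an avoidable source of bias is less useful for that choice. The plan gives no reason for protecting the motor recordings and not the photographs.

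**Working it through.** The plan gives no figure for this score, so there is no stated number to reproduce. The check is a comparison of passages, with one count.

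**1. Is it an outcome of the trial?** Yes. Section 7b lists it among the changes to be assessed.

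**2. Where does the plan place the scoring?** Four places list the score as part of a visit: the time budgets for the baseline and final evaluations, the tests due by visit 2, the visit 2 list, and the final visit list. At visit 2 and the final visit, taking the picture and scoring the birthmark are separate items on the same day's list. Item 4 of the laboratory and clinical procedures couples photograph and score in one sentence, and could equally mean scoring from the image.

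**3. Is masking described under either reading?** No.
- If the score is given during the visit, the scorer is present at a baseline or a 6-month visit of an open-label trial, and would know which.
- If the score is read later from the photographs, the plan still does not say that date and visit are hidden.

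The gap is therefore the same whichever reading is right.

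**4. Does the plan use the safeguard elsewhere?**

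| | Motor scales on video | Port-wine score |
|---|---|---|
| Status | secondary outcome | secondary outcome (7b) |
| Recorded material | video, baseline and 6 months | photographs with color chart, baseline and 6 months |
| Scorer named | occupational therapist on the team | not named |
| Blind scoring | stated | not stated |

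The plan does not say what the therapist is blind to. With one treatment arm, the only masking that helps a change score is masking of the time point. Section 4c thus does not rule out blind reading of recorded material, because section 4a already requires it.

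**5. How many photograph pairs?** Section 5 sets 10 subjects on study drug and requires brain involvement, not a facial birthmark. If k of the 10 have no facial birthmark, the paired sets number 2 × (10 − k). With k = 0 this is 2 × 10 = 20 sets, or 10 pairs, which is the ceiling. The documents do not give k.

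**6. Does timing matter?** Section 7c plans an analysis of outcome measures one year into the study, and the Milestone Table in section 7d ties an interim analysis to subjects 1–5. A masked reading has to be ready for that analysis (at most 5 pairs) and again for the final one.

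**7. Size of the bias.** No within-rater or between-rater variance and no scale range is given for this score, so no number can be put on it.

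**The case against.** The strongest reply is that the plan never says the score is given during the visit by someone who knows the time point. No scorer and no time of scoring are named. The time-commitment section is a budget for participants, not a scoring procedure. A place in a visit list does not settle when scoring happens either, since the motor video is listed too and is scored blind. The color chart suggests grading darkness from the image.

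This stands. A reader might infer from the visit lists that scoring is done face to face with the time point known. That is plausible, but the documents do not state it. The comparison with the motor video is not exact, however: the visit lists name the motor recording, whereas for the birthmark they name the score itself. In any case, the absence of a specified masked reading does not depend on this inference.

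It is also fair to say that little hangs on the score. It is absent from the hypothesis and objectives in sections 1 and 2, section 7c describes a change analysis for the cognitive score only, and entry to the extension phase does not refer to it. This keeps the point minor.

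Lastly, masking has limits here. Faces are recognisable, children from age 3 grow visibly in 6 months, and thickness may be hard to judge from a picture. These limits are real, and they bear on how far the fix helps. Because scheduled visits are by video, scoring during the visit has no clear advantage for thickness.

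**Conclusion.** The point holds as a minor one. A judged secondary outcome in an open-label single-arm trial is itemised as a visit procedure, and the plan specifies no blinded reading, although paired standardized photographs are scheduled for subjects with a facial birthmark and the plan already scores recorded motor material blind. This is more than a missing detail, because a team that follows the plan as written has nothing to keep rater expectation out of the change score.

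Three stronger readings are not supported:
- That the scorer is known to be aware of the time point: this is an inference from the visit lists.
- That 20 sets will be available: this is a ceiling, since subjects without a facial birthmark are photographed once.
- That blind reading would remove the bias at no cost: it would reduce it, at a small cost, and less so if the scorer attended the visits.

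The conclusion assumes only that the three components are rated by a person. It does not touch the cognitive primary outcome, and the size of the bias cannot be determined from the documents.

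**What to change.** Add a short statement to section 4a, item 4, and refer to it in section 7:
- Baseline and 6-month photographs of subjects with a facial birthmark (at most 10 pairs) are coded, stripped of date and visit, and put in random order.
- They are scored without knowledge of time point by an existing study team member, preferably one who did not conduct that subject's visits.
- Scoring is done in batches timed for the interim and the final analysis.
- The masked reading is the analysed port-wine score. Any score given at a visit is for information only.
- If thickness cannot be judged adequately from photographs, it is reported separately and labelled as unmasked.

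The cost is relabelling and shuffling at most 20 image sets and one scorer's reading time. No new visit, procedure or participant burden is needed. Section 8d keeps photographs until the data are analysed and published, even for participants who ask for their destruction, so the material will be available. The drawbacks are that the score may have to be split if thickness is handled separately, and that some bias may remain where a scorer recognises a face or the child's age.
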